#### 2.5 Treatment

All study participants will receive 1 unit of the study product. There is no re-dosing of the product within this study. There is no formal randomization, but both the patient and the study team will be blinded to the amount of anti-SARS-CoV-2 antibodies found in the unit of plasma assigned to the participant. The blind will be maintained until study closure and formal data analysis.

#### 2.6 Rationale for Dose

Review of the literature using COVID-19 convalescent plasma reveals that there is currently no standard dose or schedule for giving convalescent plasma. In addition there is currently no standard assay for antibody level performed on plasma in the United States and there is no way to guarantee access to more than one unit of plasma at a time or guarantee that if more than one unit were available they would be comparable in antibody content. As such the dose was chosen via the pragmatic approach of using a single unit of plasma and stratifying the results by the serological assay of that unit.

# 2.7 Study drug administration

- **1.** Plasma will be administered at an infusion rate ≤ 500 mL/hour per standards determined by the blood bank.
- 2. Pretreatment to minimize transfusion reactions (e.g. acetaminophen, diphenhydramine) may be given per investigator and clinical care team discretion.
- **3.** If an AE develops during infusion, the infusion may be slowed or stopped as per investigator's decision.
- **4.** Most reactions to plasma are relatively minor and the infusion can generally be continued. Infusion site burning and non-allergic systemic effects can generally be managed with slowing of the infusion. Infusion can generally be continued in case of itching or hives after pausing the transfusion, administering antihistamines, and observing the patient for worsening.
- **5.** Severe allergic reactions, such as bronchospasm and hypotension, may require discontinuation of the infusion.

#### 2.8 Subject Withdrawal

Taking part in this research study is completely voluntary. A participant may choose not to take part or to stop being in the study (withdraw) at any time without penalty or loss of benefits to which they are otherwise entitled, and without jeopardizing their medical care.

If a participant (or their LAR) decides to withdraw from the study they will need to notify the study PI, in writing, of their decision to stop taking part in the study. Detailed directions regarding this will be included in the consent and authorization form for the study.

Participation in this study may be stopped by the study PI or the site PI without the participant's consent for an appropriate reason, which will be explained to the participant or their LAR. Examples include:

- The study medication or procedures appear to be medically harmful to the participant.
- The participant fails to follow directions for the study.

- It is discovered the participant does not meet the study requirements.
- The study is canceled.
- It is determined to be in the participant's best interest.

Subjects who withdraw or are removed from the study will not be replaced. Discontinuation of the study: The IND holder, Beaumont Health, the FDA, the IRB, and the DSMB all have the right to terminate this study at any time.

**Secondary Outcomes:** Analyses of all secondary outcomes will use a 0.3% significance level based on the Bonferroni correction for 16 tests. Final outcome measured on a 7-point ordinal scale will be analyzed using standard linear regression,

although we will also consider proportional odds models should the range of the scale actually used be small (i.e., only 3-4 categories appear in the data). We will not use splines for the standard linear regression, but will use splines if a proportional odds model is fit to the data. We will use the same logistic regression approach as for the primary outcomes for all binary secondary outcomes (cardio-circulatory arrest, renal failure, liver failure, evidence of cytokine storm, pressor support required, and readmission).

We anticipate a small number of total number of mortality events for Group A. Should mortality for Group A be small, we will use Fisher's exact test based on categorizing the unit received by each patient as either low vs. high for amount of Anti-SARS-CoV-2-spike protein IgG. The cutoff for categorizing units will be based on either median amount or based on the cutoff determined by the Bayesian log-binomial piecewise model. For Group B, all secondary mortality outcomes will be analyzed the same as for the primary outcome. Should the number of events for any specific type of mortality (e.g., ICU mortality) prove small, we will use the approach used for analyses of Group A.

We will use a generalized linear model with splines to analyze all duration types of variables (duration of respiratory support, ICU length of stay, total length of stay). We will consider using normal, log-normal, and gamma distributions, along with appropriate links.

Type of respiratory support will be analyzed using a multinomial regression with splines for antibody amount, although we will also consider using Fisher's exact test by categorizing the unit received by each patient as either low vs. high for amount of Anti-SARS-CoV-2-spike protein IgG.

We will use either standard linear regression or Poisson regression for ventilator-free days, including splines.

We will use generalized linear mixed models to characterize changes in patient level of anti-SARS-CoV-2 IgG, and the rates, levels (based on CT values) and duration of SARS-CoV-2 RNA in nasopharyngeal swabs. These models will include time as a fixed effect, and will also include the random intercept for subject. We will also consider adding other random coefficients based on both AIC and BIC.

**Investigational Outcomes:** We will examine the relationship between primary and appropriate secondary outcomes with IgA levels as an investigational analysis using the same types of models being fit as for IgG levels.

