# **Group A Primary Efficacy Endpoint:** Avoidance of intubation at 28 days. **Group A Secondary Efficacy Endpoints:**

- **1.** Final outcome on a 7-point ordinal scale
- **2.** Cardio-circulatory arrest (at any time)
- 3. Renal failure, as measured by RIFLE criteria
- 4. Liver failure, as measured by elevation of ALT and AST to 5x the upper limit of normal or significant worsening of current liver failure with rise in transaminases of >25%
- 5. Evidence of cytokine storm based on measurement of inflammatory markers
- **6.** Type and duration of respiratory support
- 7. Requirement of pressor support
- 8. ICU mortality
- **9.** ICU length of stay
- **10.** In hospital mortality
- **11.** 28-day mortality
- **12.** Length of stay
- **13.** Ventilator-free days
- **14.** Readmission rate
- **15.** Patient level of anti-SARS-CoV-2 IgG at the following times: prior to transfusion, 1-hour post-transfusion, 24 hours post-transfusion, 72 hours post-transfusion, 7 days post-transfusion, every 7 days until discharge, day of discharge.
- **16.** Evaluate the rates, levels (based on CT values) and duration of SARS-CoV-2 RNA in nasopharyngeal swabs using RT-PCR amongst the anti-SARS-CoV-2 convalescent plasma at the following times: prior to transfusion, 24 hours post-transfusion, 72 hours post-transfusion, 7 days post-transfusion, and 14 days post-transfusion.

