#### 2.2 Data collection

The following data points will be gathered for all patients in the study while inpatient. Patients discharged prior to 28 days will receive a phone call to determine their 28 day outcome and patients enrolled in the study will be monitored for 90 days from discharge to determine if there is a readmission and the reason for the readmission.

**COVID-19 Presentation:** Collected on enrollment, see form on page 30.

**Demographics**: Collected on enrollment, see form on page 31.

Medical History: Collected on enrollment, see form on page 31.

Concomitant Medications: Collected on enrollment, see form on page 31.

Vital Signs: Collected daily from enrollment to discharge, see form on pages 30 and 32. Laboratory Values: Collected daily from enrollment to discharge, patient is required to have a CBC with differential, a CMP, a ferritin and a CRP. On enrollment and weekly the patient must have an IL-6, D-Dimer, procalcitonin, LDH, fibrinogen, ESR, and CK. IL-6 and LDH, other laboratory values will be recorded when obtained through standard of care. See form on page 32.

Clinical Status: Collected daily from enrollment to discharge, see form on page 32.

**Medications:** Collected daily from enrollment to discharge, see form on page 33.

Serology Values: Collected per schedule, see form on pages 34 and 35.

PCR Values: Collected per schedule, see form on page 36

Safety Data: Collected for first 24 hours after transfusion, see form on page 37.

**Outcomes:** Collected at discharge or death, see form on pages 38 and 39.

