#### 2.4 Schedule of events

Study Period	Screening	Baseline	Treatment		Follow Up a					
Day	-1 to 0	0	0	D	1	3	7	14	21	28
Eligibility								,	,	
Inclusion/Exclusion	Х									
Informed consent	Х									
Demographics and	V									
medical history form	X									
Initial data collection	Х									
form	^									
Type and Screen	Х									
Pregnancy Test	Х									
Study Procedures										
Plasma transfusion			X							
Vital signs			Xp							
Physical exam c	X		Xd		Χ		Χ			
Daily vital signs, clinical										
and laboratory values				Χ						
form										
Daily medications form				Χ						
Adverse event		X	X	Х						
monitoring				^						
Serology collection form		X	X		Χ	Χ	Χ	Χ	Χ	Xe
Outcome form										Xf
Laboratory Testsg				_	•	,	,			•
CBC with differential		X		Χ						
CMP		Χ		Χ						
Ferritin		Χ		Χ						
Fibrinogen		Χ					Χ	Χ	Χ	Χ
CRP		Χ		Χ			Χ	Χ	Χ	Χ
ESR		Χ					Χ	Χ	Χ	Χ
Creatine Kinase		Χ					Χ	Χ	Χ	Χ
D-Dimer		Χ					Χ	Χ	Χ	Χ
LDH		Х					Χ	Χ	Χ	Χ
Interleukin-6		X					Χ	Χ	Χ	Χ
Triglycerides		Χ					Χ	Χ	Χ	Χ
Procalcitonin		Χ					Χ	Χ	Χ	Χ
Anti-SARS-CoV-2 IgA			X h		Χ	Χ	Χ	Χ	Χ	Xi
Anti-SARS-CoV-2 IgG			X h		Χ	Χ	Χ	Χ	Χ	Xi
SARS-CoV-2 RT PCR			Xj		Χ	Χ	Χ	Χ		

- a Column D are obtained daily, day 1 and 3 are obtained 24 hours (+/- 1 hour) from transfusion end, day 7, 14, 21, and 28 are obtained any time on that calendar day.
- b Standard vital signs for transfusion of blood products will be performed.
- c Given the issues with isolation and PPE, the exam of the attending physician's team or the pulmonary critical care team can be used.
- d Only if needed due to acute reaction.
- e After 28 days will be collected every 7 days +/- 1 day till discharge.
- f Outcome form to be filled out on final day of admission if prior to 28 days or at 28 days, after 28 days a second outcome form to be filled out on final day of admission, readmission will be tracked for 90 days.
- g All laboratory tests from this list which are obtained as standard of care will be tracked, baseline labs within 24 hours are acceptable and do not need to be reordered.
- h To be drawn within 1 hour prior to transfusion and 1 hour post-transfusion completion (no earlier than 1 hour but up to 75 min post transfusion).
- i After day 28 this will be drawn every 7 days +/- 1 day while participant remains hospitalized.
- j To be obtained within 1 hour prior to transfusion.

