	Carron (1) No limitation	ig supplemental asive ventilation	O 2 or high flo	O (4) Req w O 2 device	luiring supp			
Cardio-circulatory an	` '	ys of transfusion	on: Y/N		If so c	late:		
Renal failure by RIFLE criteria within 28 days of trans				Y/N	If so c	date:		
	B days of transfu T or AST >5x three rsening of preex	ne upper limit c			If so o	late:		
Evidence of cytokine	storm based or	n inflammatory	markers:	Y/N	If so c	late:		
Days on ventilator: _	Days off	ventilator:	_ Days o	on coldflov	N:			
Days on CPAP:	Days on I	BIPAP:	Days o	Days on non-rebreather:				
Days on NC:	Days on I	Hiflo NC:	_ Discha	Discharge on new home O 2 : Y/N				
Requirement of pres	sor support: Y/N							
Pressors used	d and dates of u	se:						
In hospital mortality: Length of Stay: Readmission: Y/N	_ ICU Leng	days: Y/N th of Stay:	<del></del>			date:		
	55 4.49			<del> </del>	55 6			
Signature of coordinate	or			Date		-		

Date

Signature of Investigator reviewing data

ABACCuS Final Outcor	me Form Group A:		
Patient Initials/Study ID:		Date of Enrollment:	
Plasma Unit Used:		Date and Time of Transfusion:	
Primary Outcome:			
Was the patient intubated	d after the transfusion: Y/N		
If intubated: Da	ate of intubation:	Study Day #:	
Secondary Outcomes:			
O Hospitalized, O O	int ordinal scale: (1) No limitations on activities (3) Not requiring supplemental O (5) On non-invasive ventilation of (6) On invasive mechanical ventif (7) Deceased	$O(4)$ Re high flow $O_2$ devi	equiring supplemental O 2
Cardio-circulatory arrest after transfusion: Y/N		If so date:	
Renal failure by RIFLE criteria after transfusion: Y/N		If so date:	
	fusion: Y/N or AST >5x the upper limit of e ening of preexisting liver failure		If so date: AST of >25%: Y/N
Evidence of cytokine s	torm based on inflammatory m	arkers: Y/N	If so date:
Days on ventilator:	Days off ventilator:	Days on coldflo	ow:
Days on CPAP:	Days on BIPAP:	Days on non-rebreather:	
Days on NC: Days on Hiflo NC:		Discharge on new home O 2 : Y/N	
Requirement of presso	or support: Y/N		
Pressors used a	and dates of use:		
In hospital mortality: Y/Length of Stay: Readmission: Y/N		_	If so date:
Signature of coordinator		Date	
Signature of Investigator reviewing data		Date

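### Group A: respiratory support that continues at home after discharge is modelled as a shorter, completed duration

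*Combined protocol and SAP*

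**What the plan says.** Secondary endpoint 6 in section 2.1 is "Type and duration of respiratory support". Its start, its end and the devices that count are not defined.

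The collection window is set in section 2.2, which opens with "The following data points will be gathered for all patients in the study while inpatient". Clinical status is "Collected daily from enrollment to discharge, see form on page 32" and outcomes are "Collected at discharge or death, see form on pages 38 and 39". Note f to the schedule in section 2.4 agrees: "Outcome form to be filled out on final day of admission if prior to 28 days or at 28 days". A second form follows on the last day of admission for longer stays.

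The two Group A outcome forms ask for days on ventilator, coldflow, CPAP, BIPAP, non-rebreather, nasal cannula and high-flow cannula, so ordinary nasal oxygen counts as support. Oxygen after discharge appears only as "Discharge on new home O 2 : Y/N", with no field for days or a stop date.

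For analysis, section 3.1 states "We will use a generalized linear model with splines to analyze all duration types of variables (duration of respiratory support" and then lists ICU and total length of stay. It adds "We will consider using normal, log-normal, and gamma distributions, along with appropriate links". It names no censoring indicator, no time-to-event method and no rule for support still running at discharge.

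**The concern.** Every Group A patient enters on more than 6 L of oxygen, so leaving hospital on oxygen is a foreseeable course. The sponsor foresaw it, since the item is on the form. The recorded duration for such a patient is time to discharge, not time to the end of support, yet the model takes it as a finished value. Leaving early on oxygen can then score better than being weaned before leaving, although the second patient has come off support and the first has not.

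If antibody content affects whether or how long patients need oxygen at home, the endpoint would miss that effect or turn it around.

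**Working it through.** The plan gives no power, effect size or expected value for this endpoint, so there is no figure to reproduce. The check is of the mechanism, followed by illustrations on assumed inputs.

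**Inputs from the documents.** Collection stops at discharge (sections 2.2 and 2.4). Nasal-cannula days count and home oxygen is yes/no only (Group A outcome forms). The model is a GLM without censoring (section 3.1). Group A has 300 patients.

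**Assumed inputs.** Share sent home on new oxygen, *h*; mean further days at home, *m*; mean inpatient support of 10 days. None of these is in the documents.

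**Step 1: two hypothetical patients, days counted from transfusion.**

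| | Support ends | Discharged | Recorded | Actual |
|---|---|---|---|---|
| X | day 9, in hospital | day 10 | 9 | 9 |
| Y | day 25, at home | day 6, on oxygen | 6 | 25 |

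Recorded, Y is 3 days better than X (9 − 6). In fact Y is 16 days worse (25 − 9).

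**Step 2: the overall mean.** Shortfall = *h* × *m*.
- Low end: 0.05 × 7 = 0.35 days.
- Middle: 0.20 × 14 = 2.8 days.
- High end: 0.30 × 28 = 8.4 days.

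The high end runs past day 28. If a patient leaves on day 10 and support is counted only to day 28, at most 28 − 10 = 18 days can be added, and the high end falls to 0.30 × 18 = 5.4 days.

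**Step 3: the IgG contrast.** With a gamma GLM, a log link and a low/high IgG split, the fitted ratio is the ratio of the recorded group means.

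(a) Same share in both groups (20% and 20%), same inpatient mean. Recorded: 10/10 = 1.00. Actual: (10 + 0.2*m*)/(10 + 0.2*m*) = 1.00. No bias.

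(b) Home oxygen in 30% of low-IgG and 10% of high-IgG patients, same inpatient mean. Recorded: 1.00. Actual: (10 + 0.1*m*)/(10 + 0.3*m*).
- *m* = 7: 10.7/12.1 = 0.88
- *m* = 14: 11.4/14.2 = 0.80
- *m* = 28: 12.8/18.4 = 0.70

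A real benefit is hidden.

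(c) Equal total support, home oxygen in 10% of low-IgG and 30% of high-IgG patients, with a fraction *c* of their support seen before discharge. Actual: 1.00. Recorded: [1 − 0.3(1 − *c*)]/[1 − 0.1(1 − *c*)].
- *c* = 0.3: 0.79/0.93 = 0.85
- *c* = 0.5: 0.85/0.95 = 0.89
- *c* = 0.7: 0.91/0.97 = 0.94

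A false benefit appears.

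Simulation of these settings (300 patients split equally, 300 trials each) agreed with the formulas to within 0.01.

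In mean days, a shortfall that is equal at every IgG level cancels. On the ratio scale, dropping the same number of days from both sides leaves a ratio of 1 unchanged. It would alter the size of another ratio, but not its direction.

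**The case against.** The strongest reply is that the endpoint was never said to include oxygen at home. Data are collected during the stay, and the form keeps home oxygen apart from the device-day fields. On that reading the duration is complete at discharge and nothing is censored. This stands in part: the end point of the duration is inferred from the collection window and the forms, because the plan defines none. It does not remove the problem, since an in-hospital duration still scores early discharge on oxygen as better than weaning on the ward.

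The summary (assessment in all subjects) allows data to be supplemented by telephone, and section 2.2 plans a call for patients discharged before day 28. Neither is said to collect an oxygen stop date, and no form field or analysis rule would use one.

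It is also fair that this is part of one secondary endpoint, tested at 0.3%. The primary endpoints and the sample size are untouched.

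A reader might infer more than the documents support:
- **That the IgG result is certainly distorted, or always against high-IgG units.** Case (a) shows no bias and case (c) shows bias the other way.
- **That no analysis at all uses the home-oxygen information.** The wording of level 2 of the 7-point ordinal scale is not legible in the available text and may bear on discharged patients. The statement is safe only for the duration analysis.
- **That Group B has the same defect in its forms.** No Group B outcome form appears in the text. The collection window and the model do apply to both groups.

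**Conclusion.** The point holds for Group A. Support that continues after discharge is recorded as shorter than it was and modelled as finished, so a patient sent home on oxygen can score better than one weaned in hospital.

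Mean support is understated whenever anyone goes home on new oxygen. The documents do not allow the amount to be estimated; 0.35 to 8.4 days follows only from the assumed 5% to 30% and 7 to 28 days. That figure concerns the mean, which is not what the trial tests, and should not be read as the error in the IgG effect. The IgG association is biased only if home-oxygen use or its length varies with IgG, and the direction can be either.

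The conclusion rests on reading the duration as ending at discharge, which the collection rules and forms imply. Deaths on support need their own rule and are a separate matter.

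**What to change.** 1. Define the endpoint in section 3.1: days on support from a stated start to the end of support or day 28, with new home oxygen counted as support.
2. At the day-28 call already planned for patients discharged before day 28, ask whether new home oxygen has stopped and on what date. Add a field for the answer to the outcome form.
3. Count support to that stop date or to day 28. Treat support still ongoing at day 28 as right-censored there, and fit a log-normal or gamma model that accepts censoring. The splines for IgG can stay.
4. Where the call fails, use the existing yes/no item to mark support as unfinished at discharge and censor there, as a fallback only. Patients sent home on oxygen are selected as fit to leave, so this censoring is informative and needs a sensitivity analysis, for example one that carries support to day 28.
5. Apply the same rule to Group B if its form carries the same item.

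The cost is SAP wording, one form field, one telephone question and some recall error in the stop date. Visits and sample size do not change. The question should be in place before the calls are made, because stop dates recalled later will be less reliable or lost.

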#### 3.2 Power and sample size

We determined sample size based on a logistic regression model with a linear relationship between outcome and IgG level, and we used simulations to evaluate power for different sample sizes since we expect some sort of non-linear relationship. We assumed a piecewise model in which the probability of a good outcome increased once IgG levels were greater a threshold. Most of our power calculations used a threshold of 5 since a larger threshold resulted in slightly greater power. We expect this simulation approach to provide an estimate of the minimal power since we use a linear

relationship when the relationship is actually not linear. We assumed the baseline probability was 25% for 28-day survival and 38% for intubation rate. We selected a sample size of 200 for 28-day survival since this sample size provides excellent power (87.8%) for detecting an increase in 28-day survival to 50% (Table 1). We selected a sample size of 300 for intubation rate since this sample size provides excellent power (87.9%) to detect a decrease in intubation rate to 18% (Table 2).

Table 1. Power fo	or detecting an
increase in 28-day s	urvival when the
baseline probability	is 0.25 and the
sample size is 200.	
28-day Survival for	Power
high levels of IgG	
0.45	74.4%
0.50	87.8%

Table 2. Power f	for detecting a
decrease in intubation	on rate when the
baseline probability	is 0.38 and the
sample size is 300.	
Intubation Rate for	Power
Intubation Rate for high levels of IgG	Power
	Power 60.6%
high levels of IgG	

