#### 4.2 Potential Benefits

The potential benefits of treatment with COVID-19 convalescent plasma in patients with respiratory symptoms, requiring oxygens, and at high risk for requiring ICU admission are not known. However, it is anticipated that treatment will decrease the risk of disease progression requiring ICU admission and progression to mechanical ventilation.

The potential benefits of treatment with COVID-19 convalescent plasma in patients

already requiring mechanical ventilation are even less clear. It is anticipated that treatment will reduce the overall mortality and increase the chance of the patient no longer requiring mechanical ventilation.

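### Group A ICU days will include zeros, but two of the three distributions listed for durations cannot take zero and the plan has no rule for them

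*Combined protocol and SAP*

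**What the plan says.** Section 3.1, under Secondary Outcomes, puts the duration variables into one class of model: "We will use a generalized linear model with splines to analyze all duration types of variables (duration of respiratory support, ICU length of stay", and total length of stay. It leaves the distribution open: "We will consider using normal, log-normal, and gamma distributions, along with appropriate links". It gives no rule for choosing among the three and none for patients whose duration is zero. There is no two-part or hurdle model, no added constant, and no statement that zeros are excluded.

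Neighbouring outcomes have their own models. For ventilator-free days: "We will use either standard linear regression or Poisson regression for ventilator-free days, including splines". For type of support: "Type of respiratory support will be analyzed using a multinomial regression with splines for antibody amount". Both can use patients who were never ventilated.

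"ICU length of stay" is a listed Group A secondary endpoint (Section 2.1, item 9). The same list has type and duration of respiratory support as item 6. The Group A outcome forms record time on each device separately, including "Days on ventilator". Section 4.2 anticipates that "treatment will decrease the risk of disease progression requiring ICU admission" and progression to ventilation. Secondary outcomes are tested at 0.3%.

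**The concern.** Group A enters on more than 6 L of oxygen without intubation (Section 2.3), and the initial data form offers standard floor as a location. A patient who never goes to the ICU has exactly zero ICU days. A log-normal model needs log(0), and a gamma density requires a value above zero. An analyst who picks either must alter the zeros or leave those patients out, and leaving them out is the usual result.

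A fit to positive stays compares only patients who deteriorated. It conditions on an event that happens after transfusion and may depend on the antibody content. If plasma works by keeping patients out of the ICU, that effect is removed from the comparison. ICU length of stay is the only Group A endpoint on the list that directly counts ICU days avoided, because ICU admission itself is not listed.

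The choice of distribution therefore also decides who is analysed. AIC and BIC, which the plan uses elsewhere to select models, cannot fairly compare fits made to different sets of patients.

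**Working it through.** **The plan's own figure.** No power is stated for ICU stay or ventilator days. The nearest stated figure is the Group A primary: N = 300, baseline intubation 38%, and 87.9% power "to detect a decrease in intubation rate to 18"%. The documents do not give the IgG distribution, so this cannot be reproduced exactly. A two-proportion formula gives 87.0% if 20% of patients are above the threshold, 89.4% if 22% are, and 97.4% if 50% are. A linear-logistic simulation with threshold 5 gives 77% to 93% over seven assumed IgG distributions. The figure is plausible. The secondary level checks: 0.05/16 = 0.003125, or 0.3%.

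**How many zeros.** The expected number never ventilated is 300 × (1 − intubation rate).
- All low IgG: 300 × 0.62 = 186
- Half and half: 300 × (1 − 0.28) = 216
- All high IgG: 300 × 0.82 = 246

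So 62% to 82% of Group A would have zero ventilator days on the plan's own rates. The zero fraction for ICU days cannot be computed, because no ICU rate is given.

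**What a positives-only fit estimates.** Assume a mean of 12 days among users, the same at high and low IgG, and 38% v 18% with any use.
- All patients: 0.38 × 12 = 4.56 v 0.18 × 12 = 2.16, a difference of −2.4 days
- Users only: 12 v 12, a difference of 0

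**Power by simulation.** Assumptions: 150 low-IgG and 150 high-IgG patients; positive stays gamma with mean about 10 days and shape 1.5, equal in both halves; level 0.3%. The rank test stands in for a cumulative-link model, since it is the corresponding test for two groups. I re-ran all three scenarios under these assumptions and obtained figures within about three percentage points of those below.

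| Any stay, low v high IgG | Log-normal, positives only | Normal, all | Two-part, all | Rank, all |
|---|---|---|---|---|
| 38% v 18% | 0.4% | 46% | 73% | 81% |
| 60% v 40% | 0.4% | 26% | 60% | 61% |
| 80% v 60% | 0.4% | 21% | 72% | 54% |

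The positives-only column is null by construction: positive stays were set equal, so it can only return roughly the test level. It shows that the avoided-stay effect is outside what that model estimates. It does not measure efficiency. The useful comparison is among the last three columns. In each scenario both methods suited to zeros beat the normal model, and neither of the two is best throughout.

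A separate simulation of ventilator days (mean 12, shape 2, 38% v 18%) gave 51% for the normal model on all 300 at the 0.3% level and 85% at the 5% level. Gamma on the roughly 84 positives gave 0.6% and 6%.

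**The case against.** The strongest reply is that the plan lists the normal distribution first, says only that the three will be considered, and has all data examined graphically before modelling. A normal model keeps every zero, and a large spike would be seen before a family was chosen. That stands, so this is a gap in the plan and not a stated error. It does not close the gap: stay data are usually right-skewed, which pushes the choice towards gamma or log-normal, and the normal option loses power in every scenario tried.

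Some stronger readings are tempting but not supported.
- A reader might infer that the plan drops patients with zero days. No passage says so. It is what usually follows from choosing one of two listed families.
- A reader might infer that the benefit the trial looks for disappears. It does not. Avoided intubation is the Group A primary endpoint, and the intubation outcome has a logistic model that keeps everyone (Section 3.1 labels that outcome Group B, which I read as Group A). Ventilator-free days and type of support also keep never-ventilated patients.
- A reader might take ventilator days to be a named duration outcome with 62% to 82% zeros. Section 3.1 names duration of respiratory support, which is above zero at entry for every Group A patient. Days on a ventilator appear only as a form field, so the point reaches them only if durations are analysed device by device.
- A reader might expect high IgG to appear to lengthen ICU stay. That needs prevention to fall mainly on short stays, and nothing in the documents indicates this.

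The simulations also split IgG into halves, while the plan models it continuously with splines. The power figures are therefore illustrative.

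**Conclusion.** The point holds in limited form. For Group A ICU length of stay, and for device-specific days if these are analysed, two of the three candidate distributions cannot use patients with zero days, and the plan does not say what happens to them. Choosing log-normal or gamma would in practice limit the analysis to patients who deteriorated and lose the avoided-ICU benefit. Choosing normal keeps that benefit but costs power: about 46% against 73% to 81% at the 0.3% level, if 38% v 18% have any stay.

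The ICU rates, the even IgG split and the stay distribution are assumptions. The ordering of the normal model below the other two held at all three pairs of rates tried. Group B, total length of stay, overall duration of support and the outcomes with their own models are not affected. This is a cheap improvement to a secondary analysis and should be made before unblinding. It does not threaten the primary result.

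**What to change.** In Section 3.1, Secondary Outcomes, state that Group A ICU days, and days on any single device if analysed, are compared in all Group A patients with zeros kept. Name one method in advance:
- a two-part model, with logistic regression for any use and a gamma model for days above zero, and one joint test of IgG across both parts; or
- a cumulative-link (proportional-odds) model on days, with zero as the lowest value.

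Whichever is chosen, report mean days over all patients by IgG level beside the test. Keep gamma or log-normal for durations that are positive for everyone, such as total length of stay. Carry the same rule to the IgA analyses, which reuse these models.

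The cost is a few sentences and slightly more code. The effect measure is also less direct than a ratio of mean days: an odds ratio from the cumulative-link model, or two components from the two-part model. That is why the overall means should be shown.
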